After baseline assessment, participants will be randomized in a 1:1 ratio to the intervention or active control group using stratified block randomization. Stratification will be based on baseline HbA1c levels (6.5–9% and > 9%) to ensure balanced glycemic status across groups. The randomization list will be generated by an independent researcher. Participants will not be explicitly informed of their group allocation (single-blind design); however, due to the nature of the intervention, the research team delivering the DSMES program cannot be blinded.

Intervention Group: Nurse-Led Digital DSMES Program

Participants in the intervention group will receive a 12-week nurse-led digital DSMES program delivered through a dedicated digital platform. The program is structured according to the ADCES7™ self-care behavior framework (healthy coping, healthy eating, being active, monitoring, taking medication, problem solving, and reducing risks). Key components of the program include:

1. Structured Digital Education Modules: Educational content on T2DM pathophysiology, treatment, self-monitoring, nutrition, physical activity, medication adherence, complication prevention, and psychosocial coping strategies, presented in user-friendly language with visual aids.
2. Interactive Self-Monitoring Tools: Digital forms and tracking cards that allow participants to record glycemic values (fasting and postprandial glucose), HbA1c (when available), blood pressure (if applicable), and self-care behaviors related to the ADCES7™ domains. Participants will receive automated reminders to encourage regular data entry.
3. Nurse-Led Individualized Counseling and Support: Regularly scheduled synchronous and asynchronous communications (such as messaging or calls) with a nurse trained in diabetes education. The nurse will review participants' data, provide tailored feedback, reinforce educational messages, support goal-setting and problem solving, and offer motivational encouragement.
4. Digital Support and Chatbot: A chatbot or FAQ component to provide quick answers to common questions about diabetes management, medication use, hypoglycemia management, and lifestyle behaviors, supplementing nurse support.

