5. Multidisciplinary Collaboration (as needed): When necessary, participants may be guided to consult their physician, dietitian, or psychologist for issues identified during the digital follow-up. The nurse will facilitate communication and encourage participants to seek appropriate in-person or telehealth services.

Participants in the intervention group will be encouraged to engage with the platform regularly, follow the educational modules according to the suggested schedule, record their data, and communicate with the nurse as needed.

Active Control Group: Standard Digital Education

Participants in the active control group will be provided with access to the standard Type 2 Diabetes Education Brochure prepared by the Turkish Ministry of Health in PDF format via the digital platform. They will also be able to enter their basic glycemic data into the system. However, they will not receive individualized nurse-led digital counseling, structured DSMES modules based on ADCES7™, or chatbot-based interactive support. This design allows comparison of the comprehensive nurse-led digital DSMES program with standard digitally delivered education materials.

Outcome Measures

Primary and secondary outcomes will be assessed at baseline (pre-intervention) and at the end of the 12-week intervention.

Primary Outcomes:

1. Self-Management: Assessed using the Type 2 Diabetes Self-Management Scale, which evaluates key aspects of diabetes self-care behaviors.
2. Glycemic Control: Assessed by HbA1c levels obtained from laboratory records.

Secondary

Outcomes:

1. Diabetes Distress: Measured using the Diabetes Distress Scale.
2. Additional Glycemic Parameters: Fasting plasma glucose and postprandial plasma glucose values.
3. Self-Management Behaviors: Assessed using the ADCES7™ Self-Management Behaviors Assessment Form and the Type 2 Diabetes Personal Behavior Goal Tracking Card.
4. Metabolic Parameters: Documented with the Type 2 Diabetes Metabolic Parameter Tracking Form and Metabolic Parameter Goal Tracking Card.
5. Usability and Acceptability of the Digital DSMES Program: Assessed using the Mobile Application Usability Scale (MAUS) among participants in the intervention group.

Ethical Considerations

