The study protocol has been reviewed and approved by the Akdeniz University Faculty of Medicine Clinical Research Ethics Committee (Approval No: TBAEK-1079) and by the relevant institutional authorities at Van Regional Training and Research Hospital. All participants will be informed about the purpose, procedures, potential risks, and benefits of

the study and will provide informed consent before enrollment. Participation is voluntary, and participants may withdraw from the study at any time without any impact on their routine medical care.

Data confidentiality and privacy will be strictly protected. Personal data and clinical information will be stored securely and used only for research purposes in accordance with applicable ethical and legal regulations. The study involves a behavioral and educational intervention considered to be low risk. Adverse events related to the intervention are not expected; however, any unexpected problems will be documented and managed according to institutional policies.

Expected Contribution

It is anticipated that the nurse-led digital DSMES program will significantly improve diabetes self-management behaviors, enhance glycemic control, and reduce diabetes-related distress in young adults with T2DM compared with standard digital education alone. The results of this study may provide evidence to support the integration of nurse-led digital DSMES into routine care for young adults with T2DM, contribute to the development of innovative education models in diabetes nursing, and inform health policy and clinical practice regarding the use of digital health technologies in chronic disease management.

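### Minor: secondary outcome 3 is assessed partly with a goal tracking card, while tracking cards and goal-setting are described only as parts of the tested program

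*Protocol*

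**What the plan says.** Protocol, Outcome Measures, Secondary Outcomes, item 3 names two instruments for self-management behaviors: the ADCES7 "Self-Management Behaviors Assessment Form and the Type 2 Diabetes Personal Behavior Goal Tracking Card". The opening sentence of Outcome Measures has all primary and secondary outcomes assessed before the intervention and at the end of the 12 weeks. Item 3 carries no restriction to one arm. Item 5, the usability scale, is expressly confined to the intervention group.

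The section on the intervention group describes tracking cards as key component 2 of the program: "Digital forms and tracking cards that allow participants to record glycemic values (fasting and postprandial glucose"), continuing with "HbA1c (when available), blood pressure (if applicable), and self-care behaviors related to the" ADCES7 domains. The same item adds: "Participants will receive automated reminders to encourage regular data entry". Component 3 has the nurse review participants' data, give feedback, and "support goal-setting and problem solving, and offer motivational encouragement". The closing paragraph on this arm sets out what is asked of its members: "intervention group will be encouraged to engage with the platform regularly, follow the educational modules according to the suggested schedule, record their data". Contact with the nurse when required is mentioned there too.

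The section on the active control group gives access to a PDF brochure and allows entry of basic glycemic values. It expressly withholds nurse counseling, the structured modules and the chatbot. It neither grants nor withholds tracking cards.

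**The concern.** An outcome used to compare arms should be measured by something that stands apart from the treatment. Here, prompted recording of self-care behaviors and support for setting goals are part of what is being tested, and a card for tracking behavior goals is then one of two instruments for judging its effect.

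An intervention participant who fills in such a card at week 12 does so after 12 weeks of encouraged recording, automated reminders, nurse review and goal-setting help. For a control participant, the protocol describes none of these. A difference between arms on the card could then mix familiarity with this kind of tool and real change in behavior. At stake is how a result on half of the instruments for outcome 3 can be read.

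**Working it through.** No arithmetic applies: the protocol gives no figure for this outcome, and the point depends on no sample size, variance or effect assumption. The check is a cross-reading of the sections.

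1. **Is outcome 3 comparative?** The general sentence on assessment times covers all outcomes, and item 3 names no arm. Item 5 shows that the protocol states a restriction when one is meant. Outcome 3 therefore reads as a comparison between arms, on both of its instruments.

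2. **Where do tracking cards and goal-setting appear?** Apart from the names of the outcome instruments, tracking cards appear only in component 2 and goal-setting only in component 3, both within the intervention group's program. Reminders to enter data also appear only there.

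3. **What is described for control?** Entry of basic glycemic values, and nothing on behaviors, goals or reminders. The list of what control does not receive leaves out tracking cards, so the text is silent on whether control uses them.

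4. **Is the named card one of the component 2 cards?** The protocol does not say so. Three things point that way: the shared term, the overlap in subject (component 2 covers self-care behaviors) and the placing of goal-setting solely in the program. This remains an inference.

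5. **Does the point survive if the inference is wrong, or if both arms complete the card?** Yes, in a weaker form. A different card would still follow 12 weeks of tracking and goal work described for one arm only. If control completes the card at both assessments, no data are missing, but prior exposure to this kind of tool would still differ.

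6. **How far does it reach?** Outcome 3 has two instruments, and one is the goal card. The two primary outcomes are a self-management scale and HbA1c; neither uses the card. The card's content and scoring are not given, so neither the size of a bias nor its certainty can be established.

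**The case against.** The strongest reply is that nothing here is shown to go wrong. Both arms may complete the card at baseline and week 12 under the general assessment sentence, the card may not be a program tool, and its scoring is unknown. This stands against any claim of certain bias. It does not remove the imbalance in exposure that the text itself describes.

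A second reply is that tool practice and behavior change are not cleanly separate: monitoring and problem solving are among the seven ADCES7 behaviors, so more recording and goal work is partly what the program aims for. This stands in part. It is also a reason to treat card use as evidence of engagement and to rest the comparison on another measure.

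A third reply is that the ADCES7 form may share the difficulty, since component 2 speaks of digital forms as well as cards and covers the same behaviors. This is fair. The form cannot be declared free of the problem, and the fix has to keep it apart from routine platform entries.

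A fourth is that the statistical analysis plan, which is not at hand, may settle the matter. The choice of outcome instrument belongs in the protocol, and an analysis plan could at most restrict how the card is used.

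**Conclusion.** The point holds as a minor one, for secondary outcome 3 only. As written, the protocol makes a tool that appears tied to the treatment one of two instruments for a comparison between arms, and a difference on that card could partly reflect exposure to the program. This rests on two things that the protocol leaves open: whether the named card is one of the program's tracking cards, and whether and how control completes it. The size of any bias cannot be computed.

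Three stronger readings are not supported:

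- **That control lacks the card, so its data will be missing.** The protocol nowhere says so.
- **That the metabolic parameters in outcome 4 come from different sources in the two arms.** A reader might infer this because HbA1c as a primary outcome has a stated source ("Assessed by HbA1c levels obtained from laboratory records") and outcome 4 has none. But outcome 4 names a recording form without arm restriction, and nothing says that its values are self-entered. That is an unstated detail, not a demonstrated defect.
- **That the range of data each arm may enter on the platform measures the bias.** It describes routine entry, not who completes outcome instruments at the two assessments.

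**What to change.** In Outcome Measures, Secondary Outcomes, item 3, name the ADCES7 assessment form as the comparative measure. State that both arms complete it in the same way at baseline and week 12, as an assessment separate from entries on the platform. Report data from the Personal Behavior Goal Tracking Card descriptively, as process or engagement data, and not as a measure of the effect between arms.

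No new instrument is needed, because the form is already named. There are two costs. The card is lost as a comparative outcome; if both arms were in fact to complete it, some comparative information is given up. The outcome wording must also be amended in a protocol that already has ethics approval (Ethical Considerations: "The study protocol has been reviewed and approved by" the ethics committee).

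### Harms are recorded by an unspecific rule with no collection common to both arms, so they are likely to be under-recorded overall and captured more fully in the intervention arm

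*Protocol*

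**What the plan says.** Harms are dealt with in one sentence of the protocol, under Ethical Considerations: "Adverse events related to the intervention are not expected; however, any unexpected problems will be documented and managed according to institutional policies". The sentence before it describes the intervention as low risk. No events, definitions, collection times or procedure for asking participants are given.

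Under Intervention Group, item 3 provides "Regularly scheduled synchronous and asynchronous communications (such as messaging or calls) with a nurse trained in diabetes education" and adds that "The nurse will review participants' data, provide tailored feedback, reinforce educational messages". Item 4 provides a chatbot or FAQ component for "common questions about diabetes management, medication use, hypoglycemia management, and lifestyle behaviors".

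Under Active Control Group, participants receive a PDF brochure through the platform. Of data entry it says: "They will also be able to enter their basic glycemic data into the system". It then states: "However, they will not receive individualized nurse-led digital counseling, structured DSMES modules based on ADCES7™, or chatbot-based interactive support". No review of the control entries is described.

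Under Outcome Measures, the schedule for both arms is: "Primary and secondary outcomes will be assessed at baseline (pre-intervention) and at the end of the 12-week intervention". None of the listed outcomes is a harm or hypoglycaemia measure.

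**The concern.** Two features of the harms rule are badly fixed.

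First, its scope is ambiguous. The program teaches glucose monitoring and medication adherence, and it treats hypoglycaemia management as a topic participants will commonly ask about. One person applying the rule could log a hypoglycaemic episode as an unexpected problem. Another could leave it out as a familiar part of diabetes.

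Second, the protocol describes no route by which problems come to notice equally in the two arms. An intervention participant speaks or writes to a nurse on a schedule, and that nurse looks at the entered values. A control participant has no such contact.

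What is at stake is how the safety record can be read. Few recorded events might mean only that nobody asked. An excess in the intervention arm might mean only that this arm had someone to tell. The section on expected contribution looks ahead to supporting routine use, and a balanced case for that needs a harms record that can be interpreted. A later analysis plan cannot supply it, because events that were never collected cannot be recovered.

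**Working it through.** The protocol gives no event rate, no baseline glucose-lowering treatment and no safety figure, so there is nothing to reproduce. The check is a comparison of the text, followed by an illustration on assumed values.

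**Routes by which a harm could become known**

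- Scheduled nurse contact: intervention yes (item 3); control no ("they will not receive individualized nurse-led digital counseling").
- Review of entered data: intervention yes, by the nurse (item 3); control entry is possible but no review is stated.
- Baseline and week-12 assessments: both arms, but no harms question is attached.
- Volunteered report: possible in either arm.

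The two routes with regular contact or review are stated for one arm only. The one scheduled contact shared by both arms is not used for harms.

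**What this does to recorded counts**

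Inputs: 72 participants (Study Design) randomized 1:1 (Randomization and Blinding), so about 72 / 2 = 36 per arm. Assumed, not from the documents: a common true risk p over 12 weeks, and capture probabilities c1 (intervention) and c0 (control).

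Expected recorded cases = 36 × p × c. With the same p in both arms, the apparent ratio is (36 × p × c1) / (36 × p × c0) = c1 / c0. The true risk cancels, so only the unknown capture probabilities matter. Taking p = 20% for the counts:

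| c1 | c0 | Ratio c1 / c0 | Recorded cases, intervention v control |
|---|---|---|---|
| 0.9 | 0.9 | 1.0 | 6.48 v 6.48 |
| 0.9 | 0.6 | 1.5 | 6.48 v 4.32 |
| 0.9 | 0.3 | 3.0 | 6.48 v 2.16 |
| 0.8 | 0.2 | 4.0 | 5.76 v 1.44 |

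The true number in each row is 36 × 0.20 = 7.2 per arm.

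**What an empty record would mean**

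The chance that the control arm records no case is (1 − p × c0)^36. With c0 = 0.3 this is 58% at p = 5%, 33% at 10%, 11% at 20% and 3% at 30%.

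If 0 of 36 are recorded, the upper two-sided 95% limit on the recorded risk is 1 − 0.025^(1/36) = 9.7%. That is a limit on p × c, so the limit on the true risk is 9.7% / c. This is 9.7% with complete capture and complete follow-up, about 16% at c = 0.6 and about 32% at c = 0.3. With c unknown, an empty record bounds nothing useful.

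**The case against.** The strongest reply is that the sentence under Ethical Considerations does not restrict recording. It does not contain the word only. If intervention-related events are not expected, then one that occurs is naturally an unexpected problem and is documented. Covering hypoglycaemia management in a chatbot is general diabetes education and does not say that the program is expected to cause episodes. This stands. A reader might infer that the harms rule contradicts the intervention description and excludes hypoglycaemia, but the documents do not support that, because the two texts can both be true. What remains is an ambiguity that should be reconciled.

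Control participants are also not invisible. They attend the same two assessments, may enter glucose values and can volunteer a problem. The withdrawal criteria, which apply to everyone, include new health conditions judged by the investigator. The institutional policies, which are not shown, may add reporting steps. This also stands, and it is why unequal capture is likely and not certain. None of these routes, however, is stated to involve asking both arms the same thing.

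Finally, no between-arm comparison of harms is planned, and the low-risk wording is an ethics description, not a hypothesis under test. That limits the weight of the point but does not remove it, because the events will still be recorded and read.

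**Conclusion.** The point holds as a modest one. As written, the rule leaves it unclear whether hypoglycaemia is recorded. It also makes harms likely to be under-recorded overall and recorded more fully in the intervention arm. This rests on the assumption that scheduled contact and data review bring more events to notice than unsolicited reporting does, and that the unseen institutional policies do not already impose equal questioning.

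The size cannot be derived from the documents. A reader might take the 4-fold ratio above as an estimate of the bias. It is not one: it is 0.80 divided by 0.20, both assumed, and equal capture gives 1.0. Nor do the documents establish that hypoglycaemia is the main harm in this sample, since they give neither treatments nor event rates.

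A reader might also infer that the efficacy results are compromised. The stated primary and secondary outcomes are not affected by this rule. The consequence is narrower: the recorded events could not support the low-risk description or a balanced case for routine use.

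**What to change.** Replace the sentence under Ethical Considerations with a recording rule that is identical in both arms:

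- At the existing baseline and week-12 assessments, ask every participant the same short fixed questions on hypoglycaemia, unplanned care visits and other adverse events, over a defined recall period.
- Report the answers descriptively by arm.
- Document events learned through nurse contact or platform entries as well, but report them separately from the solicited answers.
- Reword the statement about what is expected so that it is clear, alongside the hypoglycaemia content of item 4, that such episodes are recorded.

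The cost is a minor ethics amendment, a few extra questions at two assessments already planned, and one descriptive table. Two limits remain. With about 36 per arm, any comparison will be imprecise. Equal questions also do not guarantee equal recall, because the intervention teaches monitoring and covers hypoglycaemia, so its participants may recognise and remember more episodes. The change concerns recording and reporting only, and no clinical rule is proposed.
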